STUDY PROTOCOL AND STATISTICAL ANALYSIS PLAN

Title: mHealth for Psychosis Help-Seeking

ClinicalTrials.gov Identifier: NCT05905601

Principal Investigator: [name].

Updated June 27, 2025

OVERVIEW

Study Objectives. A long duration of untreated illness is linked with poorer outcomes among youth experiencing early psychosis. While this population faces numerous barriers to in-person services (e.g. long travel distances, a lack of symptom recognition, stigmatizing attitudes toward help-seeking) most young people express interest in digital technologies to support their mental health. While multiple digital mental health interventions have demonstrated value in supporting self-management of individuals experiencing symptoms of psychosis, there is a need for new interventions designed for delivery to those who are not engaged with services but are seeking resources to learn more about their experiences online. The present study examines the acceptability, usability, and preliminary efficacy of the NORTH mHealth intervention, a mobile app designed to remotely and scalably provide support to young adults in need of evaluation or treatment for symptoms of early psychosis. This intervention, which was developed in a multi-phase user-centered design process, offers multimedia interactive content based on the principles of cognitive behavior therapy and motivational enhancement. Following an experimental therapeutics paradigm, this study examines two versions of the NORTH mHealth intervention: (1) NORTH “lite” – a version of NORTH that provides only self-management components, and (2) NORTH “full” – a version of NORTH that offers components designed to increase treatment motivation, including interactive psychoeducational information about diagnoses, treatments, and the treatment-seeking process. This study aims to examine whether the promise of mHealth can be leveraged to improve treatment-seeking attitudes and actions among this at-risk population.

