Design. This is a parallel group randomized controlled trial design. Participants are randomized 1:1 to either NORTH “lite” or NORTH “full.” Randomization is stratified based on whether the individual had engaged in mental health treatment (per inclusion criterion i.e. either regular psychotherapy or antipsychotic medication) within the past year vs. longer than one year ago (or not at all). Primary outcome assessments are collected at (1) baseline, (2) 6 weeks after app installation, and (3) 12 weeks after app installation.

METHODS

Participants. Participants are 60 treatment-unengaged young adults experiencing psychosis symptoms indicating need for evaluation and/or treatment who meet the following criteria: (1) age 18-30, (2) living in the US, (3) owning an iPhone, (4) symptoms of psychosis as measured by both (4a) a score ≥ 20 on the Prodromal Questionnaire, Brief (PQB), (4b) a positive frequency average score ≥ 1.47 on the Community Assessment of Psychic Experiences (CAPE-P15), and (4c) a score ≤ 8 on the Moritz CAPE lie scale designed for online data collection, (5) less than five years since a first episode of psychosis or awareness of symptom onset, and (6) unengaged in specialty mental health services in the previous three months as defined either (6a) having taken a prescribed antipsychotic medication, (6b) or having attended regular psychotherapy. Exclusion criteria included (1) failure to accurately complete consent comprehension questions or (2) being unengaged in mental health services because of having completed or “graduated” from a specialty mental health program.

Recruitment. Participants are recruited through online study ads (i.e. Google, Instagram, and YouTube) as well as distribution through mental health advocacy organization and treatment websites and listservs.

Procedures. All screeners and study questionnaires are completed through online data capture (i.e. REDCap). Once participants click a link to the study landing page from a recruitment ad or posting, they are required to demonstrate understanding of study details through a comprehension questionnaire, provide informed consent and are subject to a series of steps to ensure eligibility for the study and identity verification. Study team members evaluate screening data and conduct

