confirmatory synchronous screening by phone. The invitation to complete the baseline assessment is sent to participants after eligibility confirmation via text message. After baseline is complete, participants are invited to complete an installation session wherein they are introduced to their intervention, and oriented to study details. Participants are randomized to condition (via a pre-set stratified randomization algorithm, see above) at the time of the installation session.

Once participants have installed and been oriented to their study app, members of the study team are available to answer questions about study interventions or respond to concerns about the study. Up to three times during the study period, participants receive outreach via text message and phone call if they stopped using the app for five consecutive days (confirmed via app usage logs). This outreach assesses for technical issues or concerns from participants about app use. Subsequent assessments are sent to participants via text messages 6 and 12 weeks after they installed the NORTH app, and participants are also invited to complete weekly questionnaires to report actual treatment engagement frequency. Participants are compensated with \$60 gift cards for completing each assessment battery (or, in the case of baseline, baseline and installation session both).

Interventions. NORTH (Normalizing ORientation to Treatment and Help-Seeking) is a self-guided iOS mobile app designed to provide self-guided coping support to individuals experiencing early psychosis. It combines video, audio, and written text, and draws on principles of cognitive behavior therapy and motivational enhancement. While both NORTH “full” and NORTH “lite” contain lessons (i.e. introductory modules to new skills), practices (i.e. opportunities to practice skills through video coaching or written prompts), and tracking (i.e. rating changes in a well-being score over time), only participants with NORTH “full” receive in-app treatment-seeking and psychoeducational content. Note that all participants regardless of condition receive thorough materials about mental health symptoms, treatment options, and crisis resources. For participants in the NORTH “full” condition, treatment-seeking and in-depth psychoeducation is a focus of interactive mHealth content, whereas in the “lite” arm, only the self-management components can be found in-app.

Outcome Measures. Primary and secondary registered measures are listed below.

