Modified Usability Scale	Intervention Acceptability / Usability	Usability/Acceptability will be assessed with a modified version of the System Usability Scale derived from our group's previous work developing mHealth interventions. This composite measure, which comprises 26 items based on four measures - the System Usability Scale, Post Study System Usability Scale, Technology Assessment Model Measurement Scales, and Usefulness, Satisfaction and Ease Questionnaire - assesses participants' experiences with the intervention during the study period (1 = Disagree, 2 = Neutral, 3 = Agree). While this measure is often interpreted qualitatively by item, we will also compare the overall score, which will comprise an average and thus range from 1 to 3, with higher scores reflecting higher acceptability and usability.	6 weeks

DATA ANALYTIC PLAN

Clinical-trial data analyses. Linear regression will be used for continuous outcomes wherein participant and treatment condition are clustered as independent variables (i.e. adjusting for the baseline value of the outcome measure relevant to each model). We will separately model outcomes at 6 weeks and 12 weeks respectively. Within-condition changes will also be modeled using linear regression with assessment and value at baseline as independent variables. Effect sizes will be estimated using Cohen's d and 95% confidence intervals. Mean imputation is used to generate total scale scores consistent with measure convention (i.e. totaling sums or means) in instances when participants complete fewer than 50% of scale items. Descriptive outcome measures (i.e. measures of usability and acceptability) will be described qualitatively as well as compared with independent-samples t-tests. As this is a pilot trial with limited statistical power, we will model and interpret direction and size of effects for primary outcomes.

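### Acceptability is a stated aim but rests on one 6-week self-report scale with no rule for unreturned surveys; the usage logs are left out of the outcomes and the t-test omits the randomization stratum

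*Combined protocol and SAP*

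**What the plan says.** The Overview gives acceptability equal standing with efficacy: "The present study examines the acceptability, usability, and preliminary efficacy of the NORTH mHealth intervention".

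The Outcome Measures table lists one instrument for this aim: "Usability/Acceptability will be assessed with a modified version of the System Usability Scale". It has 26 items, its overall score is an average from 1 to 3, and it is collected at 6 weeks only. Every other listed measure is collected at baseline, 6 and 12 weeks.

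The analysis is one sentence in the Data Analytic Plan: "Descriptive outcome measures (i.e. measures of usability and acceptability) will be described qualitatively as well as compared with independent-samples t-tests". The only missing-data rule there concerns items within a scale. No analysis set is named for the usability score, and nothing is said about a participant who returns no survey at week 6.

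Two kinds of information already in the study play no part in this analysis. Under Procedures, participants are contacted up to three times "if they stopped using the app for five consecutive days (confirmed via app usage logs"; that is the only stated use of the logs. Under Design, "Randomization is stratified based on whether the individual had engaged in mental health treatment" within the past year, as against longer ago or not at all.

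**The concern.** The app is self-guided and is offered to people selected for not being engaged in services. In that setting, stopping use is evidence about acceptability, and the plan expects it to happen, since it provides for outreach when it does. Yet disengagement can reach the acceptability result only through a returned survey. If those who stop using the app answer less often and would have rated it lower, the responder mean is too favourable. If response also differs between NORTH full and NORTH lite, the comparison of arms is distorted too.

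A second and smaller matter is the test itself. When arms are balanced within strata, an unadjusted t-test leaves between-stratum variation in its error term even though the design has removed that variation from the arm difference. The interval is then wider than it need be. The error is on the conservative side.

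**Working it through.** **Inputs from the documents.** Overview: acceptability is an aim. Participants: "Participants are 60 treatment-unengaged young adults experiencing psychosis symptoms". Design: 1:1 allocation, so 60 / 2 = 30 per arm, with one two-level stratification factor. Outcome Measures: score range 1–3, at 6 weeks. The documents give no expected response rate, no SD for the score, no stratum sizes and no precision target, so there is no figure of the plan's own to reproduce. Every input below that is marked assumed is for illustration.

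**Step 1. Responder-only mean.** Let *m* be the share not responding and *g* the responder mean minus the mean non-responders would have given. Then

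overstatement = *m* × *g*.

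- Assumed *m* = 0.20, *g* = 0.5 points: 0.20 × 0.5 = 0.10.
- Low end, *m* = 0.10, *g* = 0.3: 0.03.
- High end, *m* = 0.30, *g* = 0.8: 0.24.

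The scale spans 3 − 1 = 2 points, so 0.10 is 5% of its range and 0.24 is 12%.

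**Step 2. Comparison of arms.** With the same *g* in both arms, the bias in the difference is (*m*₁ − *m*₂) × *g*. Assumed 30% and 10% non-response with *g* = 0.5 gives (0.30 − 0.10) × 0.5 = 0.10. With equal non-response and equal *g*, it is zero.

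**Step 3. Stratum omitted from the t-test.** Let *d* be the difference between strata in within-stratum SDs, and *q* the share in one stratum. With arms balanced within strata, the t-test uses variance 1 + *q*(1 − *q*)*d*² where 1 is correct, so the interval is too wide by the factor √(1 + *q*(1 − *q*)*d*²). For equal strata this is √(1 + *d*²/4).

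| Assumed *d* | Equal strata | 80/20 split | Simulated type I error, equal strata |
|---|---|---|---|
| 0.3 | √1.0225 = 1.01 | √1.0144 = 1.01 | 0.049 |
| 0.5 | √1.0625 = 1.03 | √1.0400 = 1.02 | 0.043 |
| 0.8 | √1.1600 = 1.08 | √1.1024 = 1.05 | 0.034 |

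The type I error column comes from 40,000 simulated trials per row with N = 60 and full response, at a nominal 5% (simulation error about 0.001).

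**Step 4. What adjustment returns.** With assumed 80% response (24 per arm) and *R*² the share of variance explained by stratum, the standard error is multiplied by √((1 − *R*²)(2*n* − 2)/(2*n* − 3)), with 2*n* = 48:

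- *R*² = 0.01: √(0.99 × 46/45) = 1.006, a loss of 0.6%.
- *R*² = 0.05: 0.985, a gain of 1.5%.
- *R*² = 0.10: 0.959, a gain of 4.1%.

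**Step 5. What the logs could show.** For a proportion still using the app, assumed to be 0.70, the 95% half-width is 1.96 × √(0.70 × 0.30 / *n*). That is 16.4 percentage points for one arm of 30 and 11.6 for all 60. If only the 48 responders were counted, it would be 13.0. The precision gain is small; the main value is that people who return no survey are represented.

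**The case against.** The strongest reply is that bias has not been shown. Stopping the app and not returning the survey are separate events. Assessments are sent by text message, completed online and compensated with \$60 gift cards, with no stated link to app use, and idle users are contacted. Some people who have abandoned the app will therefore answer. This stands: the documents support possible overstatement, not a finding that the result is biased upward, and the sizes in steps 1 and 2 rest wholly on assumed inputs.

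A reader might also infer that the logs are complete for everyone randomized. The documents do not say so. Procedures shows only that logs confirm five idle days; it does not state their content, their duration or that they cover every participant. Randomization takes place at the installation session, so someone who does not finish installing may have no log.

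Nor does the t-test alone decide acceptability. The plan calls these outcomes descriptive and also describes them qualitatively, and the test only compares arms. The qualitative description does, however, use the same returned surveys, so it does not answer the question of selection.

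Finally, usage is engagement, not opinion. Outreach can raise it, and lower use of NORTH full could follow from moving on to treatment, which that version is meant to encourage. Logs would also leave any non-response bias in the survey score where it is. All of this stands, and it limits the logs to a supplementary role. The measures table covers registered outcomes, so usage may still be reported; the gap is that this is not prespecified.

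**Conclusion.** The concern holds in a limited form. A stated aim depends on one self-report scale at one time point, with neither an analysis set nor a rule for missing surveys, while usage information already kept is not planned as an outcome. The responder mean may overstate acceptability: by 0.10 on the 1–3 scale under the illustrative assumptions, and by 0.03 to 0.24 across 10–30% non-response and gaps of 0.3–0.8 points. A 20-point difference in non-response between arms would create a spurious difference of 0.10 if the gap is 0.5.

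Omitting the stratum is minor. The interval is about 1–8% too wide for assumed stratum differences of 0.3–0.8 SD with equal strata, and about 1–5% with an 80/20 split. A reader might infer that the test is invalid or gives too many false positives. It does not: its type I error falls slightly below 5%. For a descriptive outcome in a pilot that acknowledges limited power, this costs a little precision and nothing more.

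**What to change.** 1. Replace the t-test with a linear regression of the usability score on arm plus the randomization stratum. This needs no new data. The expected gain in precision is small, and if the stratum explains almost none of the variance there is a negligible loss (0.6% in the standard error at *R*² = 0.01).

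2. State the analysis set for the 6-week usability score, and report the week-6 response rate by arm beside it.

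3. Prespecify a supplementary engagement measure, reported by arm for all randomized participants: days of use, proportion still using the app at weeks 6 and 12, and number of outreach contacts. Count anyone who never installed the app as no use. Define still using in advance; the five-idle-day rule already in Procedures is one available basis. Confirm first that the logs run to week 12 in both arms, and report any gaps in them.

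The cost is a little more analysis of data the study already monitors, and the figures may look less favourable. Usage should be presented as engagement that outreach can influence, beside perceived acceptability and not in its place.
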